### 11.1 Sample Size and Power

Forty-five (45) patients <18 years of age will be randomized at an experimental to control allocation of 2 to 1 in order to obtain approximately 36 completers, assuming an approximate drop-out rate of 20%. Subjects <18 years of age will be randomized according one age stratification factor, i.e. <10, and 10 to <18 years of age. This stratification factor is based on Kamath et al. (2020), showing an increase in the prevalence and severity of pruritus in children <10 years of age. At a 1-sided significance level of  $\alpha_{1\text{-sided}} = 0.025$ , assuming a pooled standard deviation (SD) of 1.0, and a difference between the treatment groups of 1.2 in change of pruritus, favoring response, the power of the study is 0.909, using the exact method (Proc Power, SAS v.9.4, Cary, NC). The key secondary endpoint is also powered for a standardized treatment effect (treatment effect/SD) of 1.2.

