1.1 Study Design

This is a phase 3, double-blind, randomized, placebo-controlled study to investigate the efficacy and safety of 120 µg/kg/day odevixibat compared to placebo in patients with Alagille syndrome (ALGS).

Figure 1 – Study Design

Odevixibat = once daily treatment with 120 µg/kg/day odevixibat

The study includes a screening period of up to 56 days, followed by a 24-week treatment period, and a Safety Follow-up Period. Eligible patients will be randomized 2:1 to receive odevixibat 120 µg/kg/day or placebo. An Interactive Web Response System (IWRS) will be used to assign patients to treatment. The randomization codes were computer generated by a qualified randomization vendor. An experimental cohort of approximately 45 patients <18 years of age at randomization with a genetically confirmed diagnosis of ALGS will be enrolled. Patients <18 years of age will be randomized according to an age stratification factor, i.e., <10, and 10 to <18 years of age. The protocol included an additional exploratory cohort of patients ≥18 years of age with a genetically confirmed diagnosis of ALGS, not to exceed 18 patients in total, who were also to be randomized 2:1 favoring active treatment. A separate randomization scheme was provided for this cohort. There were no subjects enrolled in this cohort at the time enrollment completed for the study.

Patients who complete the Week 24/EOT visit in this study will be invited to participate in an open-label extension study in which all patients will receive active treatment. Patients who enroll in the open-label extension study will not participate in the Safety Follow-up Period.

There will be two treatment groups in this study, odevixibat 120 µg/kg/day and placebo. Odevixibat and placebo will be supplied as capsules for oral administration. The number of capsules provided to the patient will be based on body weight at randomization (Study Day 1) and can be adjusted depending on the patient’s weight (Protocol Table 2) at each study visit.

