Age is the stratification factor for the study. Since the purpose of stratification in the randomization is to balance the treatments in each stratum and following the intend-to-treat principle, for any analysis based on the FAS where strata is used for covariate adjustment of the modeling (with the exception of subgroup analyses), the strata of age that is recorded in the randomization system (IWRS) will be used. For all other analyses based on the FAS and all subgroup analyses, the actual age will be used to categorize the age groups.

Selected patient data, including derived data, will be presented in individual patient data listings. All listings will be sorted by treatment group, patient number, date/time and visit. Each patient’s sex and age at randomization will be stated on each listing. Data listings will be based on all randomized patients.

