4.6.4.1 Continuous Endpoints

Change in ALT, AST, gamma-glutamyl transferase, direct, total bilirubin and total cholesterol, change in itching score to Month 6 (Weeks 21 to 24) as measured by the Albireo PRO instrument, change in sleep parameters, and change in growth will also be analyzed using the MMRM model. The summary of change from baseline based on MMRM model will also be displayed using graphical presentations except for itching score as measured by the Albireo PRO instrument. MMRM model will include the baseline value of the response variable, baseline age stratification, baseline direct bilirubin (for change in itching score), treatment group, visit (in months for itching score and sleep parameters, and in weeks for other assessments) and treatment-by-visit interaction. The approach to selection of the covariance matrix in the model will follow the same approach as for the primary endpoint.

The change from baseline through Week 24 in the Albireo ObsRO scratching severity scores and PRO itching scores for the morning assessment, evening assessment, and average morning and evening assessment will also be evaluated by weekly score. These endpoints will be assessed combining age groups and by age group (based on the actual age), 0 to $<$ 8, 8 to $<$ 12, and 12 to $<$ 18. A line graph of scratching daily severity scores (average AM and PM) from the Albireo ObsRO and sBA over time for each patient will be provided. In addition, line plot for mean of change from baseline on Albireo ObsRO average AM and PM, AM, and PM scratching weekly score will be provided, respectively.

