4.6.4.2 Categorical Endpoints

A clinically meaningful decrease in scratching score will be defined in the psychometric analysis report based on psychometric analysis results before database lock. Please refer to the

psychometric analysis plan for details. The results of the blinded psychometric analysis across all anchors and timepoints supported a threshold from 1.0 to 1.5 points. The upper bound of 1.5 points reduction will be used for the primary analysis while the lower bound of 1.0-point reduction will be used for the sensitivity analysis. The proportion of patients achieving a clinically meaningful decrease in scratching score (pruritus responders) at Week 24 (or Week 12) will be analyzed using a Cochran-Mantel-Haenszel (CMH) test. Patients with missing data at Week 24 (or Week 12) will be classified as non-responders. CMH stratified by baseline age stratification will be performed to compare the proportion of the responders in pruritus at Week 24 (or Week 12). In the CMH test, data in a stratum will not be used in the calculation of the p-value if a row sum or column sum is 0 in the contingency table. If a row sum or column sum is 0 or a stratum has <4 patients, the CMH test will not be stratified.

The clinician xanthoma scale uses a 5-point scale, in which 0 represents no evidence of xanthomatosis, 1 represents fewer than 20 scattered individual lesions, 2 represents more than 20 lesions that do not interfere with or limit activities, 3 represents large numbers of lesions that by their large numbers or size cause distortion of the face or extremities, and 4 represents xanthomas that interfere with function (such as hand use or ability to walk) because of excess size or number. The change from baseline to Week 12, Week 24 and last assessment during treatment in xanthomatosis will be summarized by a shift table. Shift tables for the number of patients with changes from baseline to the best and to the worst post-baseline value will be provided.

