Patients (≥ 8 years of age), caregivers, and clinicians will complete GIC (PGIC, CaGIC, and CGIC) and the GIS measures (PGIS, CaGIS, CGIS) (Protocol Appendix 3) at randomization (Study Day 1; PGIS only), Week 4, 12, and 24. The GIC items that assess change in itch (patient version), scratching (caregiver and clinician version), and sleep (all version) will be analyzed using the proportional odds model with treatment and baseline GIS score as the covariates and will consider 3 categories (better, no change, worse). The better category will include answers of “Very Much Better”, “Much Better”, and “A Little Better”; no change will include answers of “No Change”; worse will include answers of “A Little Worse”, “Much Worse”, and “Very Much Worse”. GIC and GIS data at baseline (GIS only), Weeks 4, 12, and 24 will be summarized using frequency tables and bar chart figures.

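### The GIC model leaves out the randomisation age stratum, which can cost the caregiver and clinician comparisons power if age predicts GIC after baseline GIS

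*SAP*

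**What the plan says.** SAP 4.6.4.2 specifies a "proportional odds model with treatment and baseline GIS score as the covariates" for the change items and "will consider 3 categories (better, no change, worse"). The sample code for this model in SAP 5.6 is blacked out. That section says the covariates follow the SAP text, so the list in 4.6.4.2 governs.

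On age, SAP 1.1 states: "Patients <18 years of age will be randomized according to an age stratification factor, i.e., <10, and 10 to <18 years of age". SAP 4.1 repeats: "Age is the stratification factor for the study". Protocol 11.1 justifies the factor by a cited study "showing an increase in the prevalence and severity of pruritus in children <10 years of age".

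The neighbouring analyses carry the stratum. In SAP 4.6.4.1 the "MMRM model will include the baseline value of the response variable, baseline age stratification", and in SAP 4.6.4.2 itself "CMH stratified by baseline age stratification will be performed" for the responder endpoint. The primary MMRM (4.5.2.1), the key secondary MMRM (4.6.2.1) and the rank ANCOVA (4.6.2.3.1) also include it. The PedsQL ANCOVA (4.6.4.1) uses its own age categories.

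**The concern.** Stratified randomisation balances the arms within age groups. If age also predicts the outcome, that balance makes the treatment comparison more precise. A model without the stratum does not credit this: its standard error is too large for the design, its test rejects too seldom under the null, and power is lost.

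The GIC model is the one whole-population efficacy model in the SAP with no age term. The only stated reason for removing age anywhere is small sample size, in the SAP version history, and it concerns the subgroup models. What is at stake is some power for a supportive endpoint. There is no risk of a false positive from the omission.

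**Working it through.** **1. The plan's own figure.** The only stated power is for the primary endpoint. With 24 against 12 completers, difference 1.2 and SD 1.0, the noncentrality is 1.2 × √(24 × 12 / 36) = 3.39 on 34 degrees of freedom. At one-sided 0.025 the power is 0.9094, matching the stated 0.909, and 36 / (1 − 0.20) = 45. The documents give no power or effect size for GIC, so the rest depends on assumptions.

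**2. Model simulated.** For three ordered categories,

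logit P(Y ≤ k) = α_k + β·treatment + γ·age stratum + δ·baseline GIS, k = 1, 2.

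- From the documents: 45 patients, 2:1 allocation, two age strata, three categories, baseline GIS as covariate.
- Assumed: 60% aged <10, randomised 18:9 and 12:6 within strata; γ from 0 to 2; β = 0, 1.5 or 2; δ = 0.5 per SD, with GIS independent of age; α = −0.5 and 1.5. When γ = 0, a placebo patient at average GIS then has probabilities of about 38% better, 44% no change and 18% worse.
- Each setting has 4,000 trials and a two-sided 5% Wald test. The Monte Carlo standard error is √(0.05 × 0.95 / 4000) = 0.3 points for type I error and √(0.65 × 0.35 / 4000) = 0.8 points for power.

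**3. Results, without / with the age stratum (power at β = 1.5).**

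| Age log OR γ (OR) | Type I error, % | Power, % | Difference in power |
|---|---|---|---|
| 0 (1.0) | 5.1 / 5.3 | 65.4 / 66.3 | 0.9 |
| 0.5 (1.6) | 5.1 / 5.8 | 64.4 / 65.6 | 1.2 |
| 1 (2.7) | 4.3 / 5.4 | 61.3 / 64.5 | 3.2 |
| 1.5 (4.5) | 3.4 / 5.4 | 57.0 / 63.6 | 6.6 |
| 2 (7.4) | 2.5 / 5.0 | 51.1 / 61.5 | 10.4 |

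In the top rows, part of the small difference reflects the slightly higher type I error of the adjusted Wald test.

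**4. Other settings.**
- With β = 2, the power differences across the five values of γ are 0.8, 1.0, 1.9, 3.8 and 7.2 points.
- With 36 patients and β = 1.5, they are 0.4, 2.0, 3.5, 5.6 and 9.7 points. Type I error without the stratum falls from 5.2% to 2.5%.
- With 80% aged <10, type I error without the stratum is 5.7% at γ = 0 and 3.7% at γ = 2. With the stratum it is 5.5% to 6.2%.

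**5. Source of the conservatism.** When randomisation is not balanced by age, the model without the stratum has type I error 5.2%, 5.3% and 5.1% at γ = 0, 1 and 2. The conservatism therefore comes from stratifying and then ignoring the stratum.

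**6. Patient version.** Only patients aged 8 or over answer PGIC, so its <10 stratum holds only 8- and 9-year-olds. Assume 18 such patients, a third of them 8 or 9, without exact balance by stratum (3,000 trials per setting):
- Wald type I error is 4.1% to 4.3% without the stratum and 3.9% to 4.8% with it.
- Wald power at β = 2, for γ = 0, 1 and 2, is 31.7%, 30.0% and 29.9% without, against 25.5%, 23.7% and 21.1% with.
- The likelihood-ratio test gains 0.5 to about 5 points of power from the stratum, but its type I error is then about 9%.

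**The case against.** The strongest reply is that the loss rests on a quantity the documents do not give: the effect of age on GIC after baseline GIS. Protocol 11.1 speaks of how common and severe pruritus is under age 10. That is a symptom level, whereas GIC measures change on treatment. The model already adjusts for baseline severity, and every patient must enter with an average score of at least 2. The larger losses need a residual age odds ratio of 4.5 to 7.4, which nothing in the documents supports. This stands, and the point is conditional for that reason.

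A reader might go further in four ways, none of which the documents support.

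- *The test is conservative as a matter of fact.* If age has no residual effect, type I error is 5.1% and almost nothing is lost.
- *The SAP breaks its own rule.* SAP 4.1 says which age value to use where strata are adjusted for. It does not require adjustment in every model.
- *The age term is free for all three raters.* In the PGIC example it lowered Wald power.
- *The odds ratio is biased.* Without the stratum the median estimated log odds ratio at β = 1.5 falls from 1.58 at γ = 0 to 1.30 at γ = 2. This is the difference between a marginal and a conditional odds ratio, and it is not an error in the test.

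Figures for the seven raw response options without baseline GIS would also mislead. With an assumed placebo distribution, treatment odds ratio 5 and stratum odds ratio 6, rank tests on seven categories give power 0.70 unadjusted against 0.78 stratified. Collapsing the same distribution to the SAP's three categories gives 0.51 against 0.56.

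**Conclusion.** The omission is real, unexplained and out of line with the SAP's other main efficacy models. Its cost is conditional: negligible if age has little residual effect, about 3 power points at an age odds ratio of 2.7, and 7 to 10 points only at 4.5 to 7.4. These sizes rest on the assumed treatment effect, category split, age mix and independence of GIS from age. The direction is firmer: under age-stratified randomisation, the omission made the test conservative and never inflated it in the all-age simulations.

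The conclusion applies to CaGIC and CGIC, which cover all ages and supply four of the six change items (scratching and sleep for each rater). It does not extend to PGIC. The weight is low: under SAP 4.7 the endpoint is supportive and outside the testing hierarchy.

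**What to change.** In SAP 4.6.4.2, specify by rater:

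- *CaGIC and CGIC: terms for treatment, baseline GIS score and the age stratum recorded in IWRS. If a stratum has fewer than 4 patients or the model does not converge, the age term is dropped.*
- *PGIC: terms for treatment and baseline GIS score only.*

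The threshold of 4 matches the fallback already written for the CMH test in the same section. If the sponsor prefers to leave age out, one sentence giving the reason would close the point.

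The cost is one covariate and one degree of freedom. Wald type I error with the term reached 5.8% in the main setting. It reached 6.2% with 80% aged <10, where the plan's model was already at 5.7%.

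While editing, reconcile which GIS versions are collected on Day 1. SAP 4.6.4.2 and Protocol 9.2.5 limit it to PGIS, whereas Protocol Table 1 and 7.1.2.2.1 list all three, and the model needs a baseline GIS for each rater.

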4.6.4.3 Biomarkers

Blood samples for autotaxin and p-C4 will be drawn at randomization (Study Day 1), Week 12, and Week 24, only for children with body weight >10 kg. For biochemical markers and measures of bile acid synthesis, the change from baseline to Week 24 will be analyzed descriptively in addition to the actual visit values.

FGF-19 is collected when a patient meets criteria for close observation due to suspected drug-induced liver injury (DILI); the results will be provided in a listing.

4.6.4.4 Exit Interview

During the exit interview, patients (≥ 8 years of age) and caregivers will be asked to complete the exit questionnaire (Protocol Appendix 8). The answers for the first two questions on the questionnaire will be summarized using a frequency table for each combination of the answer from these two questions by the responses from patients and caregivers. The details of responses to the exit interview will be provided in a listing.

4.7 Multiplicity Adjustment for Primary and Key Secondary Endpoints

Statistical testing for the primary analysis of the primary endpoint will be performed with a 1-sided Type I error rate of 0.025. The key secondary efficacy endpoint will be assessed for statistical significance if and only if the success criterion for the primary endpoint is met. This hierarchical testing strategy prevents alpha inflation from the assessment of multiple endpoints. Other secondary efficacy endpoints will provide supportive efficacy information regarding the differences between treatment with odevixibat and placebo. No alpha adjustments will be performed for multiple comparisons when testing other secondary efficacy endpoints.

4.8 Safety Analyses

Safety criteria are as follows:

- Primary safety analysis is the incidence of TEAEs and TEAEs categorized by causality, severity, and seriousness assessments made by the investigator by comparing active arms vs. placebo. This includes liver-related mortality and liver decompensation events (protocol Section 10.2.2.3) and all-cause mortality.
- Safety will also be evaluated by the following assessments:
 - Physical examinations
 - Concomitant medications
 - Vital signs
 - Laboratory test results (including clinical chemistry, hematology, urinalysis, AFP, vitamins A and E, 25-hydroxy vitamin D, and INR)
 - Abdominal ultrasound
 - Discontinuations due to AEs

All safety analyses will be performed on the SAF unless otherwise specified, using the following common rules:

- The analysis of the safety variables will be analyzed using descriptive statistics and summaries by treatment group for each cohort.
- No inferential statistical analysis will be planned.
- For each safety variable, the last value collected prior to first dose of study drug will be used as the baseline for all analyses.

4.8.1 Adverse Events

General common rules for summarizing adverse events

All AEs will be classified by SOC and PT using the MedDRA version 25.0.

AEs will be classified as TEAEs, defined as follows: An AE (classified by preferred term) that occurs during the Treatment Period will be considered a TEAE if it has a start date on or after the first dose date of study drug, or it has a start date before the date of the first dose date of study drug but worsened in severity on or after the date of the first dose date of study drug.

AEs with missing start dates, but with stop dates either overlapping with the treatment period or missing, will be considered TEAEs. A TEAE with missing drug-relationship will be considered as related. A TEAE with missing severity will be considered as CTCAE grade 3 (severe). Details for imputing missing or partial start dates of adverse events are described in [Appendix 5](#). AEs with the same AE reference number that is collected on AE page of eCRF are counted as one AE only.

Adverse events of interest (AEIs)

Adverse events of interest (AEIs) will be selected for analyses as indicated in [Table 6 - Selections for AEIs](#).

Table 6 – Selections for AEIs

AEIs	Selection
Liver Decompensation	
a. The following TEAEs will be included:
 
PT = International normalised ratio increased and checkbox that event is refractory to vitamin supplementation is checked and at least 1 INR value (within 2 weeks [+/-] of the AE started date) is >1.5
 
PT = Vitamin K increased and checkbox that event is refractory to vitamin supplementation is checked and at least 1 INR value (within 2 weeks [+/-] of the AE started date and checkbox) is >1.5
 
PT = Hepatic failure, Acute on chronic liver failure, or Subacute hepatic failure
 
b. The following TEAEs occurring as separate events or in the presence of (i.e. ongoing medical history or AE) PT of portal hypertension and/or PT of hepatic cirrhosis were included:
 
PT = Ascites
 
PT = Hepatorenal syndrome
 
PT = Portopulmonary hypertension
 
PT = Oesophageal varices haemorrhage
 
PT = Gastric varices haemorrhage
 
PT = Intestinal varices haemorrhage
 
PT = Hepatic encephalopathy

Liver Related	
The following Standardised MedDRA Queries (SMQs) will be included:
 
 • Drug related hepatic disorders – comprehensive search SMQ (narrow and broad) • Biliary tract disorders SMQ • Gallbladder related disorders SMQ • Gallstone related disorders SMQ
FSV Deficiency refractory to clinically recommended vitamin supplementation based on CRF	Both questions of “Is this an event of fat-soluble vitamin deficiency?” and “Is this refractory to clinically recommended vitamin supplementation?” on the AE page are checked as “Yes”.
Possible Sequelae of FSV Deficiency	Specified TEAEs with PTs are listed in Appendix 10

AEIs	Selection
Clinically Significant Diarrhea	
Clinically significant diarrhea is defined as diarrhea that persists for 3 or more days without any other etiology (e.g., infection) as assessed by the investigator, diarrhea reported by the investigator as severe in intensity or reported as an SAE or diarrhea with concurrent dehydration requiring treatment with oral or intravenous rehydration and/or other treatment intervention. Therefore, at least one of the following conditions met will be considered as clinically significant diarrhea:
 
 • PT = Diarrhoea or Diarrhoea haemorrhagic, and last for ≥ 3 days and the CRF question of “Does this event have a clear etiology (e.g., Infection)?” on the AE page is checked as “No”. • PT = Diarrhoea or Diarrhoea haemorrhagic and CTCAE ≥ 3 • PT = Diarrhoea or Diarrhoea haemorrhagic and SAE = “Yes” • PT = Diarrhoea or Diarrhoea haemorrhagic and the CRF question of “Is this an event of diarrhea with concurrent dehydration requiring treatment with oral or intravenous rehydration and/or other treatment intervention?” on the AE page is checked as “Yes”

Analysis of all adverse events

An overall summary of the incidence of TEAEs (number of patients with any events and number of events, if applicable) will include the following:

- Overview of the incidence of TEAEs
- Drug-related TEAEs (AE will be defined as drug-related if causality is either probable, possibly, or definitely related)
- TEAEs by CTCAE grades 1, 2, 3, 4, 5
- TEAEs leading to study drug discontinuation
- TEAEs leading to study drug interruption
- TEAEs leading to study drug dose reduction
- Serious TEAEs
- Drug-related serious TEAEs
- TEAEs leading to death
- Any hepatic TEAE
 - Any TEAE of liver decompensation (as defined in Table 6 - Selections for AEIs, for TEAEs listed in b occurring as separate events)
 - Any TEAE of liver decompensation (as defined in Table 6 - Selections for AEIs, for TEAEs listed in b in the presence of (i.e. ongoing medical history or AE) PT of portal hypertension and/or PT of hepatic cirrhosis)
 - Any liver-related TEAE (as defined in Table 6 - Selections for AEIs)
- Any Fat-Soluble Vitamin (FSV) Deficiency refractory to clinically recommended vitamin supplementation TEAEs (as defined in Table 6 - Selections for AEIs)
- Possible Sequelae of FSV Deficiency TEAEs (as defined in Table 6 - Selections for AEIs)

- Any Clinically Significant Diarrhea TEAEs (as defined in [Table 6 - Selections for AEIs](#))
- Overview of the incidence of TEAEs by age group 1 (0 to <10, 10 to <18, based on the actual age)
- Overview of the incidence of TEAEs by age group 2 (0 to <2, 2 to <12, 12 to <18, based on the actual age)

TEAEs (number of patients with any events and number of events, if applicable) by SOC (as applicable) and PT will be tabulated for the following:

- TEAEs by SOC and PT
- All TEAEs by PT by descending incidence in odevixibat column
- TEAEs leading to study drug discontinuation by SOC and PT
- TEAEs leading to study drug interruption by SOC and PT
- TEAEs leading to study drug dose reduction by SOC and PT
- Serious TEAE by SOC and PT
- Drug-related TEAEs by SOC and PT
- Drug-related serious TEAE by SOC and PT
- TEAEs leading to death by SOC and PT
- Common TEAEs ($\geq 5\%$ odevixibat group) by PT
- Severe or worse of TEAEs (CTCAE grade ≥ 3) by SOC and PT
- Hepatic TEAEs
 - Any TEAE of liver decompensation (as defined in [Table 6 - Selections for AEIs](#), for TEAEs listed in [b](#) occurring as separate events) by SOC and PT
 - Any TEAE of liver decompensation (as defined in [Table 6 - Selections for AEIs](#), for TEAEs listed in [b](#) in the presence of (i.e. ongoing medical history or AE) PT of portal hypertension and/or PT of hepatic cirrhosis) by SOC and PT
 - Liver-related TEAEs by SOC and PT
- FSV Deficiency refractory to clinically recommended vitamin supplementation TEAEs by SOC and PT (as defined in [Table 6 - Selections for AEIs](#))
- Possible Sequelae of FSV Deficiency TEAEs by SOC and PT (as defined in [Table 6 - Selections for AEIs](#))
- Clinically Significant Diarrhea TEAEs by SOC and PT (as defined in [Table 6 - Selections for AEIs](#))

Summary tables for number of patients with any TEAEs by SOC and PT by severity (grade 1 to grade 5) and by causality (related [possibly, probably, and definitely] vs unrelated [unlikely and unrelated]), will also be provided. AEs with the worst severity will be used in the by-severity summaries. Similarly, AEs with the worst causality (most related to treatment) will be used in the by-causality summaries. If severity or causality is missing, data will be imputed as grade 3 or related, respectively.

When a patient has the same adverse event, based on preferred terminology, reported multiple times during the study, the patient will only be counted once at the preferred terminology level in adverse event frequency tables. Where a patient has multiple adverse events within the same SOC during the study, the patient will only be counted once at the SOC level in adverse event frequency tables. In the AE summaries, AEs will be sorted by alphabetically for SOC and PT.

In addition to the frequency summary of TEAE tables, the exposure adjusted incidence rate (EAIR) (per 100 patient years at risk) with the 95% confidence interval, based on Poisson distribution, will also be provided for each of the following AE tables:

- TEAEs by SOC and PT
- Liver-related TEAEs by SOC and PT
- Liver Decompensation TEAEs (as defined in [Table 6 - Selections for AEs, for TEAEs listed in b in the presence of \(i.e. ongoing medical history or AE\) PT of portal hypertension and/or PT of hepatic cirrhosis](#)) by SOC and PT
- FSV Deficiency refractory to clinically recommended vitamin supplementation TEAEs by SOC and PT
- Possible Sequelae of FSV Deficiency TEAEs by SOC and PT
- Clinically Significant Diarrhea TEAEs by SOC and PT

The EAIR (per 100 patient years at risk) will be calculated as follows:

$$\text{Number of subjects with event} / \text{Total cumulative time at risk (years)} \times 100$$

where total cumulative time at risk is the sum of individual time at risk. The time at risk for a subject with the event of interest will be calculated (in years) as:

$$(\text{first event date} - \text{date of first dose} + 1) / 365.25$$

The time at risk for a subject without the event of interest is calculated as:

$$(\text{last participation date} - \text{date of first dose} + 1) / 365.25$$

Kaplan-Meier curves may be used for time to event data (time to first liver decompensation TEAEs [as defined in [Table 6 - Selections for AEs, for TEAEs listed in b in the presence of \(i.e. ongoing medical history or AE\) PT of portal hypertension and/or PT of hepatic cirrhosis](#)] onset (days), time to first liver-related TEAEs onset (days), time to first FSV deficiency refractory to clinically recommended vitamin supplementation TEAEs onset (days), time to first possible sequelae of FSV deficiency TEAEs onset (days), time to first clinically significant diarrhea event onset (days), and time to all-cause mortality (weeks)). Patient will be censored at the last contact date if no event occurs.

A diarrhea event is defined as a TEAE with PT as Diarrhoea or Diarrhoea haemorrhagic. Descriptive summary statistics will be used to summarize the duration of each diarrhea episodes (days), the number of episodes per patient and time to onset of diarrhea (days). In addition, the summaries will be provided for clinically significant diarrhea TEAEs.

In order to assess who developed onset of FSV Deficiency refractory to clinically recommended vitamin supplementation, a listing merging with concomitant medications and selected lab data will be provided.

Analysis of special situations

Certain safety events are defined by regulatory authorities as Special Situations and require reporting. These Special Situations include:

- Overdose of study medication
- Suspected abuse/misuse of study medication
- Medication error involving the study medication
- Drug-drug interaction
- Pregnancy

Special Situations should be reported on the Special Situations page of eCRF, whether or not they result in an AE/SAE. Number (%) of patients experiencing these special situations will be provided.

